### Secondary measures

Proportion of drugs (or alcohol)-with-sex occasions (of all sex occasions) during the past 3 months is derived from the SERBAS and 8 sets of SADAR questions that have been incorporated into it. These sets reflect 8 type-of-sexual-behavior (i.e. vaginal, anal, oral passive, oral active) X partner (i.e. main, other-than-main) type combinations occurring during this time period. Each question within a set directly asks for the number of behavior type X partner type combinations that occurred under the influence of 10 different types of drugs or alcohol, as well as the total number of time the behavior type X partner type combination occurred (in general). Thus, to obtain the proportion of drugs-or-alcohol-with-sex, 2 different operations must be carried out. First, for each of the 8 (behavior type X partner type combination) sets of questions, the number of times the behavior occurred under the influence of the certain drugs (including alcohol) is summed. Second, this sum is divided by the total number of times the behavior X partner type combination occurred (in general) to obtain the proportion of time this combination occurred under the influence of drugs or alcohol. To obtain an overall proportion of all drugs-or-alcohol-with sex occasions of all sex occasions, the overall total number of times all behavior type X partner type combinations occurred under the influence of drugs or alcohol is divided by the overall total number of times that all behavior type X partner type combinations occurred (in general).

Proportion of unprotected sex occasions (of all sex occasions) during the past 3 months is derived from the studies reporting the efficacy of our study intervention (Schilling, [name], Schinke, Gordon and Nichols, 1991; [name] and Schilling, 1992).

Perceived self-efficacy to carry out safer sex will be measured by the Condom Use Self-Efficacy Scale. This consists of 11 5-point Likert scale items that measure the participant's belief in her ability to protect herself during sex and to negotiate safer sex. Perceived Self-efficacy is the total of the 11 questions; it can range from 0 – 44.

Carrying condom: Dichotomous rating of whether or not the participant is carrying condoms – assessed at 3-month and 6-month post-intervention. This is a simple dichotomous (Yes/No) rating of whether or not the subject produces condoms from his/her pockets or handbags, when asked to do so by the research assistant.

Gender role beliefs will be measured by the Bem Sex Role Inventory-Short Form (BSRI) (Bem, 1981). It consists of 30 7-point items – on which the participant can be characterized as masculine, feminine, or gender-neutral. Means scores, ranging from 1-7, are obtained for each of these categories.

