## SYNOPSIS

**Study Objectives:** Drug treatment, itself, has been a powerful deterrent to HIV drug use risk behavior. However, sexual risk behavior has received less attention and has been slower to change. The proposed study will bring [name]'s and Schilling's (Schilling et al., 1991; [name] and Schilling, 1992) proven, manual driven, gender-specific safer sexual skills building (SSB) intervention to frontline drug abuse counselors in methadone maintenance (MMTP) or outpatient drug-free treatment (ODF). The proposed study is intended to test the effectiveness of [name]'s and Schilling's safer sexual skills building group intervention to reduce unprotected sexual risk behavior in sexually active women in MMTP or in drug-free outpatient treatment. Due to the need for comparable interventions for male drug users in treatment, the proposed trial is intended for simultaneous implementation with its companion protocol for men. The concurrent delivery of 2 parallel protocols is planned as a streamlined, cost-effective way to carry out both protocols with shared research staff, materials and resources.

**Study Design:** The study will use a randomized trial to test the effectiveness of the 5 session safer sexual skills building group intervention, as compared to a 1 session group standard HIV education intervention (HE) comparison condition. A repeated measures battery will be administered at 4 points: 1) baseline; 2) immediate post- intervention (i.e. for secondary efficacy and intervention fidelity measures only); 3) 3-months post-intervention; and 4) 6-months post-intervention.

**Subject Populations:** Subjects will be approximately 480 women (i.e. 240 women/intervention condition) in methadone maintenance (N=240) or drug-free outpatient treatment (N=240) who fulfill criteria for being at heightened risk for HIV/STD heterosexual transmission. Inclusion of both MMTP and ODF will provide the opportunity to reach 2 important subgroups of female drug users: those whose primary substance of abuse is heroin (MMTP); and those whose primary substance of abuse is likely to be stimulants, alcohol or multiple drugs (ODF).

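### The drugs-or-alcohol-with-sex proportion adds counts across 10 substance types, so unless the items allow only one substance per occasion it counts some occasions more than once and can exceed 1

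*Protocol*

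**What the plan says.** Section 8.4.1 names the SADAR as the source of this secondary outcome, and section 11.3 (Secondary measures) fixes how it is derived.

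- **Question sets.** "These sets reflect 8 type-of-sexual-behavior (i.e. vaginal, anal, oral passive, oral active) X partner (i.e. main, other-than-main) type combinations".
- **Content of each set.** The woman reports how often the behaviour "occurred under the influence of 10 different types of drugs or alcohol, as well as the total number of time" it occurred at all.
- **Step 1.** Within each set, "the number of times the behavior occurred under the influence of the certain drugs (including alcohol) is summed".
- **Step 2.** Then "this sum is divided by the total number of times the behavior X partner type combination occurred", in order "to obtain the proportion of time this combination occurred under the influence of drugs or alcohol".
- **Overall measure.** The under-the-influence total, pooled over all combinations, "is divided by the overall total number of times that all behavior type X partner type combinations occurred (in general").

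Section 11.6.2 tests this quantity as Hypothesis 2, and section 11.6.3 reuses it as a putative moderator. Nowhere does the protocol give a rule for an occasion involving more than one substance. It states no any-substance item, no mutually exclusive coding, no de-duplication and no cap at 1.

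**The concern.** The two parts of the ratio use different units. A substance-by-substance count records an act once for every substance involved, while the total records it once. A single act after both alcohol and cocaine adds 2 above the line and 1 below. The result is nevertheless labelled as the share of times the act took place under the influence, and that label is right only if no act ever involves two substances.

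What is at stake is the meaning of the Hypothesis 2 result. A fall in the computed value could come from fewer substance-involved occasions, from fewer substances on the same number of occasions, or from both. The distinction matters here because the SSB sessions described in section 6.1.2 deal directly with alcohol and drug use. The intervention could plausibly change how many substances are used per occasion without changing how many occasions are affected.

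**Working it through.** The protocol states no figure for this measure, so there is nothing to reproduce. The check applies the section 11.3 rule to simple cases.

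**Inputs from the protocol (section 11.3):** 10 substance types; 8 sets; numerator = sum of per-substance counts; denominator = total occurrences.

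**Assumed inputs (not in the documents):**
- u = true share of occasions involving any substance
- m = share of those occasions involving more than one substance
- k = number of substances on each such occasion

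**Formula.** Each single-substance occasion adds 1 to the numerator and each multiple-substance occasion adds k, so

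computed value = u × [(1 − m) + m × k].

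**Results:**

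| u (true share) | k | m = 0 | m = 25% | m = 50% | m = 100% |
|---|---|---|---|---|---|
| 0.50 | 2 | 0.50 | 0.625 | 0.75 | 1.00 |
| 0.80 | 2 | 0.80 | 1.00 | 1.20 | 1.60 |
| 1.00 | 2 | 1.00 | 1.25 | 1.50 | 2.00 |
| 0.50 | 3 | 0.50 | 0.75 | 1.00 | 1.50 |

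At m = 0 the rule returns the true share. If every substance-involved occasion involves two substances, the value exceeds 1 once u is above 0.50.

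**The same thing in terms of two substances.** Suppose alcohol is used on 40% of occasions and cocaine on 40%. The rule gives 0.40 + 0.40 = 0.80. The true any-use share is 1 − 0.6 × 0.6 = 0.64 if use is independent, and 0.40 if the two always go together. At 60% and 60% the rule gives 1.20, against 1 − 0.4 × 0.4 = 0.84 or 0.60.

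**Effect on an arm comparison.** Take two arms with the same true share, 0.50, and k = 2, but with two-substance shares of 50% and 20%:
- first arm: 0.50 × (1 + 0.50) = 0.75
- second arm: 0.50 × (1 + 0.20) = 0.60

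The computed difference is 0.15, although the share of occasions under the influence is identical.

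**What per-substance counts can still give.** Within a set, the number of any-use occasions is at least the largest single-substance count and at most min(sum, total). Take 20 occasions, 16 of them substance-involved and 8 of those with two substances. The sum is 8 + 2 × 8 = 24, and the rule gives 24/20 = 1.20 where the truth is 16/20 = 0.80. If the 24 mentions fall evenly on two substances (12 each), the bounds are 12/20 = 0.60 and min(24, 20)/20 = 1.00. These contain 0.80 but do not identify it.

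**The case against.** **The instrument is not shown.** Double counting needs items that let one occasion be reported under several substances. If the 10 categories are exclusive, for instance main substance only or with a separate combination category, the sum is the correct number of occasions. This stands, and it makes the point conditional. A reader might infer that the measure is certainly wrong; the documents do not support that. They do leave the rule without the one condition that would make it right.

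**The overall measure is worded in occasions.** The sentence for the pooled proportion speaks of times the acts occurred, which may reflect an intended occasion count loosely described. That is fair as to intent. But no source for the pooled numerator is given other than the per-set sums, so the stated derivation carries over.

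**Overlap on the same occasion is not documented.** The Synopsis describes one subgroup as "those whose primary substance of abuse is likely to be stimulants, alcohol or multiple drugs (ODF"), which concerns the primary substance of abuse, not what is used together during sex. Section 5.1 describes the same group by cocaine or other stimulants only. This stands: overlap is plausible, but its rate is unknown and every rate above is assumed.

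**Both arms use the same rule, and the models adjust for baseline.** If the intervention leaves substance use with sex unchanged, the summing does not by itself create an arm difference. That also stands. The problem is interpretation when the number of substances per occasion changes.

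**Model failure.** A reader might infer that values above 1 would break the analysis model. The documents do not support that. Section 11.6.2 names linear mixed models for outcomes taken as normal, marginal logistic regression for binary outcomes and a marginal model for counts. It assigns no bounded proportion model to this outcome. A linear model would run on values above 1; it would simply be estimating a different quantity.

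**Conclusion.** The concern holds in conditional form. As section 11.3 is written, the numerator counts substance mentions and the denominator counts occasions. Unless the SADAR items restrict each occasion to one substance, the measure overstates the share of occasions under the influence, has no ceiling at 1, and combines two different behaviours in the test of Hypothesis 2. The error runs from zero with no overlap to large with heavy overlap (for example 1.20 against a true 0.80), and the documents do not show where this trial would fall.

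Because the protocol fixes this derivation itself, it is a stated rule and not a detail left for later. If only per-substance counts are collected, the any-use share can be bounded but not recovered. The outcome is one of five secondary outcomes, and neither the primary outcome nor the sample size depends on it. The change should be made, but it does not threaten the trial's main conclusion.

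**What to change.** In section 11.3, redefine the numerator as the number of occasions under the influence of any drug or alcohol, each counted once. Take it from one any-drug-or-alcohol count in each behaviour-by-partner set. The overall proportion is then the pooled any-use count divided by the pooled total.

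- **If only per-substance counts are available:** do not call their sum a proportion of occasions. For each set, report the largest single-substance count as the lower bound and min(sum, total) as the upper bound, each over the total.
- **If the SADAR categories are mutually exclusive:** state this in section 11.3. One sentence resolves the point and no new items are needed.

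The cost is 8 short ACASI items, a revised derivation and slightly more respondent time. Section 8.4.1 says these items are meant to allow comparison between the women's and men's studies, so the same items and derivation should also go into the companion men's protocol.

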#### **3.2 Secondary Objective**

Secondary outcomes will include: proportion of drugs or alcohol with sex occasions of all sex occasions; proportion of unprotected sex occasions (of all sex occasions); carrying condoms; perceived self-efficacy to carry out safer sex; and gender role beliefs. It is hypothesized that women in the SSB intervention will decrease their proportion of drugs or alcohol with sex occasions (of all sex occasions), decrease their proportion of unprotected sex occasions (of all sex occasions), increase their condom carrying, increase their sense of self-efficacy to carry out safer sex, and increase their endorsement of egalitarian gender role beliefs significantly more than women in the HIV education intervention.

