### 11.3 Efficacy Measures and Statistical Analyses

There will be one primary efficacy measure: number of unprotected penetrative (vaginal or anal) intercourse occasions during the past 3 months. This will be computed at the following assessment time points: 1) baseline; 2) 3-month post-intervention follow-up; and 3) 6-month post-intervention follow-up. The primary analysis will test the hypothesis that SSB intervention will significantly exceed HIV education in decreasing number of unprotected occasions from baseline to follow-up assessments. Possible SSB intervention effects on secondary efficacy measures will also be tested over the same time periods. These include hypothesized greater gains in self-efficacy to carry out safer sex, decrements in proportion of drugs or alcohol with sex occasions, gains in condom carrying, and change towards more egalitarian gender role beliefs in the SSB intervention condition, as compared to the HE condition.

The efficacy measures will be defined as:

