#### **11.5.7 Missing data and dropout**

We will make any effort to assess all subjects at both follow-up times (3- and 6-months post-intervention). Despite our thorough and proactive approach to taking complete measurements on all randomized study subjects at all time points, we expect that there will be cases when assessments will be incomplete or missing. The analytic strategy in such cases will depend on the nature of the missing pattern and missing data. For example if at a given assessment time a subject has all but a few items of a questionnaire, a prorated score based on the available items will be computed. As another example, when data on a subject are available only at baseline, such subject

cannot be included in the analysis since even the modern statistical methods like Longitudinal Models (described above) require observations on at least two occasions; in such case some imputation is needed for values of the outcome at follow-up. In general, we will use multiple imputation approach based on propensity scores (Lavori et al., 1995). However, for some outcome measures alternative imputation methods might be more appropriate; for example, for the dichotomous secondary outcome measure 'taking condoms from open clinic supplies' it will be more appropriate to impute 'no' for the missing value of subjects who can not be brought to the clinic for assessment.

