### 11.6.2 Secondary hypotheses

Hypothesis 2: SSB intervention will significantly outperform HE intervention with respect to decreasing the proportion of drugs-or-alcohol-with-sex occasions (of all sex occasions).

Hypothesis 3: SSB intervention will significantly outperform HE intervention with respect to decreasing the proportion of unprotected sex occasions (of all sex occasions).

Hypothesis 4: SSB intervention will significantly outperform HE intervention with respect to increasing perceived self-efficacy to carry out safer sex.

Hypothesis 5: SSB intervention will significantly outperform HE intervention with respect to increasing condom carrying.

Hypothesis 6: SSB intervention will significantly outperform HE intervention with respect to increasing the magnitude of egalitarian gender role beliefs.

Some of these outcome measures could be assumed to follow normal distribution and for them linear mixed effects models will be used test the respective hypotheses. Linear Mixed Effects Models for continuous outcome Y will be employed:

$$(2) \quad Y_{ijkt} = \beta_0 + \beta_1 X_{ijk} + \beta_2 t + \beta_3 X_{ijk} t + \gamma_1 Z_{1ijk} + \gamma_2 Z_{2ijk} + s_k + s_{kt} + c_j + \varepsilon_{it},$$

Here the variables X, Z and t are defined the same as in (1),  $s_k$  is a random effect for strata,  $s_{kt}$  is a random effect for strata by intervention interaction,  $c_j$  is a random effect for cluster and  $\varepsilon_{it}$  is an individual error term and the two error terms associated with the two measurements on the same individual will be correlated. The following assumptions

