about the random terms are made:  $s_k \sim N(0, \sigma_s^2)$ ,  $s_{kt} \sim N(0, \sigma_{st}^2)$ ,  $c_j \sim N(0, \sigma_c^2)$ ,  $\varepsilon_{it} \sim N(0, \Sigma)$  and all random terms are independent of each other and  $\Sigma$  is homoskedastic. The estimated variance of the random effects of sites by intervention ( $s_{kt}$ ) will give a measure of the variability of the intervention effects between sites. This can be compared with the estimated variance of the random site effects ( $s_{kt}$ ), which estimates the variability between sites with respect to the efficacy of the control treatment. The estimated variance of the random effects associated with cluster ( $c_j$ ) will be a measure of the variability in the outcome measure associated with intervention group within a CTP site. We anticipate that this variance will be small compared with the between CTP sites variance.

Binary outcome will be analyzed with marginal logistic regression and outcome of count will be analyzed with the marginal model similar to (1). The covariates in these regression models will be specified in the same way as in testing the primary hypothesis. GEE will be used to estimate the parameters in the marginal models.

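### Condom carrying is timed at 3 and 6 months with no baseline rating named, so its specified baseline-adjusted model cannot be fitted and change from baseline cannot be estimated

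*Protocol*

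**What the plan says.** **Measure.** Section 11.3, under Secondary measures, defines condom carrying as a "rating of whether or not the subject produces condoms from his/her pockets or handbags" when the research assistant asks. The timing given is "assessed at 3-month and 6-month post-intervention".

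**Schedule.** Table 2 (Schedule of assessment collection) has no condom-carrying row. Sections 8.4.1 to 8.4.10 describe no instrument that contains the rating. Section 8.4.5 mentions carrying only as something a woman may say when completing a vignette.

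**Hypothesis.** Section 3.2 expects women in SSB to "increase their condom carrying" more than women in HE. Section 11.6.2 states that "SSB intervention will significantly outperform HE intervention with respect to increasing condom carrying". The opening of Section 11.3 lists baseline, 3 months and 6 months for the primary measure, then says "Possible SSB intervention effects on secondary efficacy measures will also be tested over the same time periods", with condom carrying among the measures listed there.

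**Model.** Section 11.6.2 assigns binary outcomes a marginal logistic regression estimated by GEE, and adds: "The covariates in these regression models will be specified in the same way as in testing the primary hypothesis". In model (1) of Section 11.6.1 those covariates are arm (X), time (t), their product, the pre-intervention value of the outcome (Z1) and pre-intervention monogamy status (Z2).

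**The concern.** The hypothesis and the model both look back to a pre-intervention value that the data collection does not provide. A statistician who follows Section 11.6.2 literally reaches the condom-carrying analysis and finds that a required covariate is absent for every woman.

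This is more than a detail for an analysis plan to settle. The rating is made on the spot, by whether the woman produces condoms when asked, so a missed baseline cannot be reconstructed. An analysis plan could drop the covariate, but it cannot supply the observation or the schedule row. At stake are the specified adjustment, the precision it would bring and any statement about how far carrying changed.

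**Working it through.** The protocol gives no rate, effect size or power for condom carrying, so there is no figure of its own to reproduce. The check is mainly one of consistency.

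**Step 1: what the model needs.** With the covariates of model (1), the binary model is

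logit P(Y = 1) = β0 + β1 X + β2 t + β3 X·t + γ1 Z1 + γ2 Z2,

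with t = 0 at 3 months and t = 1 at 6 months. Baseline enters only through Z1.

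**Step 2: what is collected.**

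| Quantity | Needed by | Provided for |
|---|---|---|
| Y at 3 and 6 months | Section 11.6.2 | Section 11.3 definition; no Table 2 row |
| Z1, carrying before intervention | Sections 11.6.1 and 11.6.2 | Nowhere stated |
| Change from baseline | Sections 3.2 and 11.3 | Needs Z1 |

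**Step 3: consequence.** With about 480 women and two follow-up times there are at most 480 × 2 = 960 outcome records. Z1 is missing on all of them, so no record is complete and γ1 cannot be estimated. GEE tolerates missing outcomes, but not a covariate that nobody has. The multiple imputation in Section 11.5.7 does not help, because no observed baseline rating exists from which to impute.

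**Step 4: what can still be fitted.** Without Z1, the terms X, t, X·t and Z2 can all be estimated. They give the difference between arms in carrying at 3 and 6 months, not an increase from baseline.

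**Step 5: size of the precision loss.** By the usual linear approximation, adjusting for a baseline value that has correlation r with follow-up multiplies the variance of the arm comparison by 1 − r². The protocol gives no r, so the values below are assumptions.

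- r = 0.3: 1 − 0.09 = 0.91, a 9% reduction in variance; √0.91 = 0.95, so the standard error falls by about 5%.
- r = 0.5: 1 − 0.25 = 0.75, a 25% reduction; √0.75 = 0.87, so the standard error falls by about 13%.

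For a logistic model with clustering these are a guide only.

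**The case against.** Several objections carry weight.

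**Randomization protects the comparison.** A reader might infer that Hypothesis 5 cannot be tested at all, or that without baseline a chance difference between arms cannot be told from an effect. Neither follows. Hypothesis 5 compares two arms randomized within site. A follow-up comparison that allows for clustering already counts chance imbalance in its standard error. The size of such imbalance can be illustrated with 240 women per arm, an assumed carrying rate p and a design effect D = 1 + (m − 1)ρ2, using 1.96 × √(p(1 − p) × 2/240 × D):

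- p = 0.10, m = 4, ρ2 = 0.10 (D = 1.30): about 6 points
- p = 0.30, D = 1.30: about 9 points
- p = 0.30, m = 8, ρ2 = 0.15 (D = 2.05): about 12 points
- p = 0.50, D = 2.05: about 13 points

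Group sizes and ρ2 come from Section 11.2; the rates are assumptions. These differences are ordinary sampling error, not added bias. This objection stands in full.

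**The definition does not say that baseline is excluded.** The two times it names are also the outcome times of the model, and the opening of Section 11.3 implies a baseline. That is fair: the absence of a baseline rating is inferred. But nothing else in the protocol supplies one, so the text is at best inconsistent.

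**Table 2 lists instruments, not items.** SADAR and monogamy status have no row either, so a missing row does not prove that the rating goes unrecorded. This stands in part. The SADAR questions are stated to sit inside SERBAS, whereas no host form is named for this in-person observation, and the action checklists in Section 8.4.4 do not include it.

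**The missing-data text is a side issue.** Section 11.5.7 illustrates a rule with "taking condoms from open clinic supplies", which is not among this trial's secondary outcomes. A reader might infer that condom carrying has no missing-data rule. It does: multiple imputation is the general approach, and the sentence is only an example, probably a leftover label.

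**Conclusion.** The mismatch is real but limited. As specified, the baseline-adjusted GEE model for condom carrying cannot be fitted from the data the protocol provides for, and the rise from baseline that Sections 3.2 and 11.3 describe cannot be estimated. What remains is a valid randomized comparison of the proportions carrying condoms at 3 and 6 months.

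The loss in precision is 9% to 25% of variance if the baseline correlation lies between 0.3 and 0.5, and that range is an assumption. The conclusion that the model cannot be fitted depends on no assumed number. It rests only on reading the Section 11.3 timing as complete, which no other section contradicts with an actual baseline rating. The point touches one of five secondary outcomes and should be corrected because the repair is cheap and a baseline rating not taken cannot be recovered.

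**What to change.** Choose one of two courses.

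1. **Collect baseline (preferred).** Add the yes/no rating to the existing baseline visit, give it a Table 2 row at baseline, 3 and 6 months, and amend its timing in Section 11.3. The stated model and hypothesis then stand. The cost is one short observation by the research assistant. Asking at baseline might prompt women to carry condoms, but baseline precedes randomization, so any prompting should be equal in both arms.
2. **Keep follow-up only.** Add the Table 2 row at 3 and 6 months and drop Z1 for this outcome in Section 11.6.2. Restate Hypothesis 5, with the matching wording in Sections 3.2 and 11.3, as a higher proportion carrying condoms at follow-up under SSB. This costs text edits only, but gives up the precision gain and any estimate of change.

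Under either course, as a minor edit, reconcile the outcome named in the imputation example of Section 11.5.7 with the trial's own secondary outcome.
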